## **14.3 Secondary Endpoints**

Cardiac-specific mortality will be analyzed using Kaplan-Meier models to estimate median times to these events, as well as the proportion experiencing an event at 3, 6, 9 and 12 months.

Agreement between 3D and 2d echocardiogram biomarkers will be described using Bland-Altman plots, which plot the mean of two measurements on the same individual against the difference of those measurements. If the values are reasonably Gaussian, the standard  $\pm 2$  standard deviations will be used as the limits of agreement. If the values are non-Gaussian, bootstrap estimates will be used to define the limits of agreement.

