### **1.2 Treatment of Metastatic Sarcoma**

Generally, localized sarcoma is treated with surgery when feasible and adjuvant radiation with or without chemotherapy. Like any other cancer, sarcomas have the ability for hematogenous spread to develop distant metastases. For the majority of patients with metastatic soft tissue sarcoma, their cancer is incurable. Therefore, the goal of treatment is to reduce cancer bulk, minimize cancer related symptoms, improve quality of life, and increase overall survival. Despite our best efforts, the median survival of patients with distant metastases is 11 to 15 months with approximately 20-25% of patients being alive at three years .

Most cases of advanced soft tissue sarcoma are treated with conventional chemotherapy for palliation. A common treatment regimen is single agent doxorubicin. There have been many attempts to improve upon this treatment approach with dose intensification and combination therapies. A randomized trial by EORTC Soft Tissue and Bone Sarcoma Group compared doxorubicin alone, doxorubicin plus ifosfamide, and a four-drug regimen of cyclophosphamide, vincristine, doxorubicin, and dacarbazine. The combination treatment did not significantly improve overall survival (OS), progression-free survival (PFS), or response rate (RR), and these combination regimens were significantly more toxic . Another randomized phase III trial evaluated single agent doxorubicin compared to doxorubicin plus ifosfamide in advanced or metastatic soft tissue sarcoma. There was no significant difference in OS between the two treatment groups (median OS 12.8 months vs. 14.3 months, p=0.076). The combination chemotherapy group had a significantly higher PFS (7.4 months vs. 4.6 months, p 0.003) and there was a higher overall response rate in the combination treatment arm (26% vs. 14%) .

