## **2.2 Secondary Objectives**

1. To determine cardiac-related mortality in patients with metastatic soft tissue sarcoma who are treated with doxorubicin in combination with dextrazoxane.
2. To determine incidence of heart failure or cardiomyopathy in patients with metastatic soft tissue sarcoma who are treated with doxorubicin in combination with dextrazoxane.
3. To evaluate additional echocardiogram parameters of left ventricular ejection fraction to determine if either 3D echocardiogram or ventricular strain is able to serve as an early marker of cardiac dysfunction compared to 2d echocardiogram modified Simpson's biplane method of LVEF.

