### **14.2 Primary Endpoint**

We are comparing the progression-free survival (PFS) rate of patients being treated with doxorubicin in combination with dextrazoxane to a historic control established by Judson et al in 2014. PFS is defined as the time from randomization to the first occurrence of progression or death due to any cause. If no event exists, the PFS will be censored at the last scheduled disease assessment on study. Patients who have reached their maximum follow-up and have remained progression-free will be censored for progression at the date of their last disease assessment. Intention to treat principles will be used for analyzing the primary endpoint. The primary endpoint will be tested using estimates of median PFS and 95% confidence intervals derived from Kaplan-Meier models.

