### **14.3.1 Sample Size and Statistical Power**

The historic control used for comparison is based on data published by Judson et al. Patients with advanced or metastatic soft tissue sarcoma treated with single agent doxorubicin had a median PFS of 4.6 months. We consider a median PFS of 3.7 months (safety margin of 20%) to be non-inferior to the PFS seen in patients treated with doxorubicin alone. We will be using a one-sided log-rank test at an alpha level of 0.05 with a power of 0.80 to determine if treatment of doxorubicin with upfront dextrazoxane is non-inferior to doxorubicin alone.

[figure not shown]
A maximum of 65 patients may be enrolled to allow for a 10% dropout rate, resulting in at least 57 patients for testing of the primary endpoint. Using 57 patients, we have 0.80 power at a 1-sided significance level of 0.05 to detect a median PFS 3.7 months compared to this historic control's PFS of 4.6 months.

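### Section 14.3 takes the proportion of cardiac deaths from Kaplan-Meier with no rule for non-cardiac deaths; if these are censored, the proportion is overstated

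*Combined protocol and SAP*

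**What the plan says.** Section 2.2 lists as its first secondary objective "To determine cardiac-related mortality in patients with metastatic soft tissue sarcoma" treated with the combination. Section 14.3 gives the analysis: "Cardiac-specific mortality will be analyzed using Kaplan-Meier models to estimate median times to these events, as well as the proportion experiencing an event". The four landmarks are months 3, 6, 9 and 12.

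No section says whether a non-cardiac death is censored, kept in the risk set or treated as a competing event, and cumulative incidence is not mentioned. The only censoring rules in section 14 are those for PFS in section 14.2, for example "If no event exists, the PFS will be censored at the last scheduled disease assessment on study". They cannot be carried over, because any death is an event for PFS.

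On the size of the competing risk, section 1.2 states that "the median survival of patients with distant metastases is 11 to 15 months". For the cited randomised phase III trial of doxorubicin with or without ifosfamide it gives "median OS 12.8 months vs. 14.3 months".

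**The concern.** Section 14.3 asks for a proportion of patients. When other deaths are censored, Kaplan-Meier estimates something else: the risk of cardiac death if nobody could die of anything else. Patients already dead of sarcoma are represented by those still alive, as if they could still die of cardiac disease. The more non-cardiac deaths there are, the further one minus Kaplan-Meier lies above the proportion requested, and in this population most deaths will be non-cardiac.

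The study drug is a cardioprotectant, so the error would overstate the outcome the drug is meant to prevent. The planned median time to cardiac death has a separate problem: it is very unlikely to be reached.

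**Working it through.** The plan states no expected cardiac death rate, so there is no figure of its own to reproduce. The check asks what proportion of patients an assumed Kaplan-Meier value stands for.

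**Inputs.** All-cause median survival of 11 to 15 months, with 12.8 months as an intermediate value (section 1.2). Sample size 57 (section 14.3.1: "resulting in at least 57 patients for testing of the primary endpoint"). Assumed: a 12-month Kaplan-Meier value of 5% with non-cardiac deaths censored, and constant hazards.

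**Formulas.**
- Cardiac hazard: c = -ln(0.95)/12 = 0.004274 per month.
- All-cause hazard: L = ln 2 / median.
- True proportion by month t: (c/L) × (1 - exp(-L t)).

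**Month 12.** For a median of 11 months, L = 0.0630 and exp(-12 L) = 0.469, so the true proportion is (0.004274/0.0630) × 0.531 = 3.60%.

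| All-cause median (months) | Alive at 12 months | True proportion | 5% ÷ true | Gap (points) | Gap in patients of 57 |
|---|---|---|---|---|---|
| 11 | 46.9% | 3.60% | 1.39 | 1.40 | 0.80 |
| 12.8 | 52.2% | 3.77% | 1.33 | 1.23 | 0.70 |
| 15 | 57.4% | 3.94% | 1.27 | 1.06 | 0.61 |

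A simulation of 2,000,000 patients per scenario gave 3.61% and 3.94% at medians of 11 and 15 months.

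**All four landmarks**, same assumptions:

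| Month | One minus Kaplan-Meier | True proportion | Gap (points) |
|---|---|---|---|
| 3 | 1.27% | 1.17% to 1.20% | 0.08 to 0.11 |
| 6 | 2.53% | 2.14% to 2.24% | 0.29 to 0.40 |
| 9 | 3.77% | 2.94% to 3.15% | 0.63 to 0.84 |
| 12 | 5.00% | 3.60% to 3.94% | 1.06 to 1.40 |

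**Sensitivity to the assumptions.**
- *Survival shape.* Constant hazards imply 10% to 19% alive at three years, below the 20% to 25% in section 1.2. Weibull survival fitted to the stated medians and three-year figures gives a true 12-month proportion of 3.3% to 3.9%.
- *Longer survival.* The 11 to 15 months refers to distant metastases, and the trial also admits unresectable disease. At assumed medians of 18 or 24 months the relative excess falls from 27% to 39% down to 22% or 15%.
- *Timing of cardiac deaths.* With an assumed other-cause median of 12.8 months, the relative excess is 13% if all cardiac deaths fall in months 0 to 4.6, and 62% if all fall in months 6 to 12.

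**Varying the cardiac share of deaths** (assumed 2%, 5% and 10%; all-cause median 12.8 months). With share s, the Kaplan-Meier target is 1 - exp(-12 s L) and the true proportion is s × (1 - exp(-12 L)). Error figures come from 40,000 simulated trials of 57 patients with no other censoring.

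| Cardiac share | Kaplan-Meier | True | Gap (points; patients) | RMSE, Kaplan-Meier (points) | RMSE, cumulative incidence (points) | No cardiac death by month 12 |
|---|---|---|---|---|---|---|
| 2% | 1.29% | 0.96% | 0.3; 0.2 | 1.8 | 1.3 | 58% |
| 5% | 3.20% | 2.39% | 0.8; 0.5 | 2.9 | 2.0 | 26% |
| 10% | 6.29% | 4.78% | 1.5; 0.9 | 4.1 | 2.8 | 6% |

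Kaplan-Meier exceeded the crude proportion by more than one patient in 4%, 14% and 35% of these trials. Over medians of 11 to 15 months and shares of 2% to 10%, the bias runs from 0.25 to 1.98 points, or 0.1 to 1.1 patients.

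**The median.** At the hazard c above, the Kaplan-Meier median would be ln 2 / 0.004274 = 162 months, against at most 60 months of follow-up (section 5.5). In the simulated trials it was reached by month 60 in about 1%, 3% and 9% for the three shares.

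**The case against.** The plan never says that non-cardiac deaths are censored. If those patients were kept at risk to each landmark with complete follow-up, the estimate would equal the crude proportion and there would be no bias. The quarterly follow-up in section 5.5 would make that feasible. This stands: the documents establish a missing rule, and the overstatement follows only under the usual reading.

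The 5% is not a figure from the documents. It implies that 6.8% to 9.3% of deaths are cardiac, which may be high given the cardiac exclusions in section 3.2. That also stands, and is why other shares are shown. The direction does not depend on it: any cardiac death that follows a censored non-cardiac death pushes Kaplan-Meier too high.

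The practical effect is small. At 3 and 6 months the gap is at most about a quarter of one patient in 57. At a 12.8-month median, zero or one cardiac death occurs by month 12 in about 90% of trials at a 2% share and 60% at 5%; with none, both estimators give zero. No test, threshold or decision rule rests on this endpoint. All of this stands and limits the severity. It does not favour Kaplan-Meier, which under censoring is both biased and more variable than cumulative incidence.

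Finally, reporting a median as not reached is legitimate. Dropping it is a tidying step and not the core of the fix.

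**Conclusion.** The concern holds and is minor. The plan names an estimator for the proportion of cardiac deaths without a rule for the far more frequent non-cardiac deaths, and the usual application of that estimator does not give the proportion requested. With an assumed 12-month Kaplan-Meier value of 5%, an all-cause median of 11 to 15 months and constant hazards, the reported figure would be 27% to 39% above the true one. In absolute terms the bias is under one patient in 57 at a 12.8-month median for cardiac shares up to 10%, and about 1.1 patients in the most adverse combination of share and median examined. It is below sampling error. Cumulative incidence removes the bias and has about 30% lower RMSE. The primary PFS analysis is not affected.

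**What to change.** In section 14.3, replace Kaplan-Meier for cardiac-specific mortality with the Aalen-Johansen cumulative incidence of cardiac death at 3, 6, 9 and 12 months, with 95% confidence intervals, and state that non-cardiac death is a competing event. Reporting the number of cardiac deaths beside each estimate would help with so few events. The median time to cardiac death need not be planned.

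The cost is one sentence of wording. Cause of death is already needed for the planned analysis, so no data, visits or patients are added.

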### **1.3.1 Cardiotoxicity and Anthracyclines**

The most concerning toxicity of anthracyclines is cardiotoxicity. Anthracycline-induced cardiotoxicity ranges from subclinical left ventricular dysfunction to severe cardiomyopathy with heart failure. Cardiotoxicity may occur acutely within the first week of treatment, early within one year of completing therapy, or late after one year of completing anthracycline treatment.

The cardiotoxic effects of doxorubicin have been well established in studies dating back decades . The estimated incidence of heart failure for patients on doxorubicin receiving a cumulative dose of 400-550 mg/m^2 range widely from a relatively low 3-7% by Von Hoff et al 1979 to a significantly higher 27% by Speyer et al 1992. At higher doses around 1000 mg/m^2 as many as half of patients may experience the cardiotoxic effects .

The exact mechanism of anthracycline-induced cardiotoxicity is not entirely known. It has traditionally been believed that the cardiotoxic effects of have been mediated by redox cycling and the generation of reactive oxygen species; newer evidence suggests that it may be specifically mediated by topoisomerase-IIβ in cardiac myocytes . An additional mechanism may include accumulation of mitochondrial iron leading to increased reactive oxygen species inside the cardiac myocyte .

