## **5.0 TREATMENT PLAN**

### **5.1 Agent Administration**

Dexrazoxane will be given intravenously on an outpatient basis over 15 minutes on each day that doxorubicin is given. Dexrazoxane should be given no more than 30 minutes prior to administration of doxorubicin, which is typically given on Day 1 of a 21-day cycle. Dosing is a 10:1 ratio of dexrazoxane to doxorubicin; doxorubicin will be started at 75 mg/m^2, so dexrazoxane dosing would be 750 mg/m^2. Doxorubicin is being given as routine care; the administration is not dictated per protocol. Patients who are enrolled in the control group will receive institutional standard of care therapy.

In the event of a national shortage of dexrazoxane, 72-hour infusional doxorubicin can be used instead of dexrazoxane and bolus doxorubicin.

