### **5.5 Duration of Follow-up**

Patients will be followed every 3 months for up to five years or until death, whichever occurs first. Patients removed from study for unacceptable adverse events will be followed until resolution or stabilization of the adverse event. Patients who go off study due to toxicities will be followed until progression of their disease.

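### Section 14.3 prespecifies no cardiac-mortality proportion after 12 months, before the protocol's late cardiotoxicity window opens, and its planned median is unlikely to be estimable

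*Combined protocol and SAP*

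**What the plan says.** Section 2.2 sets the first secondary objective: "To determine cardiac-related mortality in patients with metastatic soft tissue sarcoma" treated with the combination. It gives no time horizon. Section 14.3 holds the whole analysis: "Cardiac-specific mortality will be analyzed using Kaplan-Meier models", which are to "estimate median times to these events, as well as the proportion experiencing an event at 3, 6, 9 and 12 months". It states neither the time origin nor how non-cardiac deaths are treated.

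Section 1.3.1 divides cardiotoxicity by timing: acute in the first week, "early within one year of completing therapy", or "late after one year of completing anthracycline treatment". Section 5.5 says: "Patients will be followed every 3 months for up to five years or until death, whichever occurs first". The study calendars in Section 10 and the Follow Up Form in Section 11 repeat the three-monthly, five-year schedule.

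**The concern.** The protocol recognises a late form of the toxicity that dexrazoxane is meant to prevent and follows patients long enough to see some of it. Yet the last prespecified proportion is at month 12, before the late period begins. The only other summary, the median, needs the estimated curve to fall to 50%. That is a lot to ask of an event that should be uncommon.

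The likely report on this objective is therefore a median that was not reached plus four early proportions. Late cardiac deaths would have no planned estimate or interval, and any later time point quoted would be picked after seeing the curve.

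**Working it through.** The plan gives no sample size, expected count or precision for cardiac mortality, so there is no figure of its own to reproduce.

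**Inputs from the documents.** Doxorubicin, "which is typically given on Day 1 of a 21-day cycle" (Section 5.1). Section 1.2: "the median survival of patients with distant metastases is 11 to 15 months with approximately 20-25% of patients being alive at three years". At least 57 treated patients (Section 14.3.1). Heart failure incidence of 3-7% in one cited study and 27% in another, at 400-550 mg/m² (Section 1.3.1).

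**Assumptions.** One to six cycles, because the protocol fixes no number. Exponential all-cause survival with median *m* of 11 or 15 months. A constant share *p* of deaths that are cardiac, ranged from 1% to 50%, because the documents give heart failure incidence but no cardiac death rate. No loss to follow-up.

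**1. When the late window opens.** Month = 12 + treatment duration. For *c* cycles, duration runs from (*c* − 1) × 21 days (last dose) to *c* × 21 days (end of last cycle), at 30.44 days per month.

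- 1 cycle: 12.0 to 12.7 months from first dose
- 4 cycles: 14.1 to 14.8 months
- 6 cycles: 15.4 to 16.1 months

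If the clock started at end of treatment, the window would open just after the last landmark. Either way, no landmark lies inside it. From first dose, the last 2 to 4 months of the early window are also missed after four to six cycles.

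**2. Patients still alive.** S(t) = 0.5^(t/*m*), times 57.

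| Month | S(t), *m* = 11 to 15 | Alive of 57 |
|---|---|---|
| 12 | 0.469 to 0.574 | 27 to 33 |
| 16 | 0.365 to 0.477 | 21 to 27 |
| 24 | 0.220 to 0.330 | 13 to 19 |
| 36 | 0.103 to 0.189 | 6 to 11 |
| 60 | 0.023 to 0.062 | 1 to 4 |

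Section 1.2's own 20-25% at three years gives 57 × 0.20 to 57 × 0.25 = 11 to 14, so the range at 36 months is 6 to 14.

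**3. Share of cardiac deaths after month 12.** With a constant hazard, the share of five-year cardiac deaths is [S(12) − S(60)] / [1 − S(60)].

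- *m* = 11: 0.446 / 0.977 = 0.46
- *m* = 15: 0.512 / 0.938 = 0.55

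At *p* = 7%, expected cardiac deaths by five years are 57 × 0.07 × 0.977 = 3.9, or 57 × 0.07 × 0.938 = 3.7. Of these, 1.8 to 2.0 fall after month 12.

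**4. Whether the median is reached.** 20,000 simulated trials of 57 patients, 60 months of follow-up, non-cardiac deaths censored:

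| Cardiac share of deaths (assumed) | Probability that the median is reached, *m* = 15 to 11 |
|---|---|
| 1% | 0.2 to 1.0% |
| 3% | 0.4 to 2.9% |
| 7% | 1.8 to 8.0% |
| 15% | 12 to 30% |
| 27% | 56 to 77% |
| 50% | over 99% |

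At 7%, a median that is reached typically rests on about 2 patients at risk, at 50 to 55 months. If non-cardiac death is a competing event instead, the crude incidence reaches 50% with probability about 0 up to a 27% share.

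**5. Why later landmarks need competing risks.** With non-cardiac deaths censored, Kaplan-Meier targets 1 − 0.5^(*p*t/*m*). The proportion who actually die of a cardiac cause is *p* × (1 − 0.5^(t/*m*)). At *p* = 7%:

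- 24 months: 10.0% against 5.5% (*m* = 11); 7.5% against 4.7% (*m* = 15)
- 36 months: 14.7% against 6.3% (*m* = 11); 11.0% against 5.7% (*m* = 15)

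Adding late landmarks to a curve that censors non-cardiac deaths would thus roughly double the apparent risk by 36 months.

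**The case against.** Two stronger readings are tempting. The documents support neither.

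- A reader might infer that the median cannot be reached. It can: with non-cardiac deaths censored, the curve may cross 50% as the risk set shrinks, and it usually does if 27% or more of deaths are cardiac. That end of the range is extreme, since it amounts to treating the highest heart failure rate cited at 400-550 mg/m² as always fatal.
- A reader might infer that five years of follow-up produce no reported result. Section 14.3 does not truncate the Kaplan-Meier analysis at 12 months, so later deaths enter the curve and the median. The same follow-up also supplies progression and death for the primary endpoint.

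The case for leaving the plan alone is that the objective states no horizon, the early/late split is background rather than an endpoint definition, and landmarks to 12 months are defensible when median survival is 11 to 15 months. The endpoint is descriptive, and later values could be read from the curve. This limits the severity but does not remove the gap: values chosen afterwards are not prespecified, and with non-cardiac deaths censored they would overstate risk.

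It can also be said that late cause of death may not be collected. Adverse events are tracked for only 30 days after treatment (Section 7.4), the follow-up column in Section 10 lists only history, physical examination and performance status, and the content of the Follow Up Form is not given. So it cannot be claimed that the documents show the data exist. But the planned 9- and 12-month figures already need cause of death well beyond that 30-day window for a patient treated for, say, six cycles.

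**Conclusion.** The concern holds in limited form. No cardiac-mortality proportion after 12 months is prespecified, and the late window opens only after the last landmark under either time origin considered. That part is timing arithmetic and needs no assumption about event rates.

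That the median is very unlikely to be reached, and unstable if it is, depends on a low cardiac share: at most about 8% at a share of 7% or less. That about half of five-year cardiac deaths fall after month 12 depends on a constant hazard. The numbers alive depend on the survival figures in Section 1.2 and on complete follow-up. Losses would reduce the numbers at risk.

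This is a worthwhile, inexpensive improvement to a secondary safety objective. It does not affect the primary analysis.

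**What to change.** In Section 14.3:

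- Remove the median time to cardiac death as a summary.
- State first dose as the time origin.
- Keep 3, 6, 9 and 12 months and add 24 and 36 months.
- Report each as cumulative incidence of cardiac death, with non-cardiac death as a competing event, a 95% interval and the number at risk.
- Do not add a 60-month landmark, which would rest on about 1 to 4 patients.

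The cost is a few lines of analysis text and a different estimator. No extra patients or visits are needed. The sponsor should confirm that the Follow Up Form records cause of death, which the present 12-month figure already needs. The downside is imprecision at 24 and 36 months, which the intervals and numbers at risk will make plain.

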### **1.7 Amendment #9—Removal of Olaratumab**

In January 2019 Eli Lilly and Company reported that the results of the Phase 3 study of olaratumab (Lartruvo), in combination with doxorubicin in patients with advanced or metastatic soft tissue sarcoma, did not confirm the clinical benefit of olaratumab in combination with doxorubicin as compared to doxorubicin alone. Therefore olaratumab is being removed from the front line standard of care regimen. Amendment #9 was made to the protocol to reflect these changes to the standard of care treatment. Section 9.1 was also updated to clarify 9.1 the evaluation of cardiac function using echocardiogram and the addition of 10 sarcoma banking protocol #201203042 participants to be used as controls in the secondary objectives analysis.

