## **9.0 CORRELATIVE STUDIES**

### **9.1 Evaluation of Cardiac Function with Echocardiogram**

Patients receiving dexrazoxane will undergo cardiac evaluation with echocardiograms every six weeks to evaluate for cardiac function.

Left ventricular ejection fraction (LVEF) will be evaluated by 2D echocardiogram by modified Simpson's biplane method will be provided to investigators within two days of the evaluation. Treatment decisions regarding cardiac safety will be determined by a decrease in LVEF by 2D echocardiogram (modified Simpson's biplane method) based on the clinical reading.

In addition, cardiac function will be evaluated using these images and interpreted by offline research echocardiographic laboratory and this interpretation will not be made available to the treating physicians, however the PI will have access for non-clinical purposes. Left ventricular systolic function will also be evaluated by 3D echocardiogram when technically possible.

Left ventricular diastolic function will be evaluated by mitral inflow pulsed wave Doppler to evaluate the mitral E velocity, mitral E deceleration time and mitral A velocity. Tissue Doppler imaging of the mitral annulus will also be evaluated. Load Independent Index of Filling (LIIF) will be measured. It should be noted that this has never been done outside a research laboratory. This measurement in this part of the protocol is experimental.

Right ventricular systolic function will be measured and cardiac valves will be evaluated. The additional cardiac measurements, specifically 3D echocardiogram calculated ejection

fraction, left ventricular strain, will be used to evaluate for an early or more precise measurement of cardiac dysfunction.

Additional controls for these analyses will be collected from the sarcoma banking study (HRPO #201203042) under a waiver of consent. Identifiers will be collected in order to perform the chart review. The chart review will be performed to assess for cardiac function and symptomatic heart failure.

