## 10.2 CONTROL ARM

Baseline/screening procedures may take place up to 14 days prior to the start of treatment, except consent and scans (including the echocardiogram and Holter monitor), which may take place up to 28 days prior to the start of treatment.

	Baseline / Screening	Day 1 of Each Cycle	Day 1 of Each Odd-Numbered Cycle	End of Each Even-Numbered Cycle	EOT	F/U
Informed consent	X					
H&P, ECOG PS	X				X	X
CBC	X					
CMP	X					
β-hCG 	X					
2D and 3D echocardiogram	X		X 			
CT C/A/P	X			X	X	
Dexrazoxane 		Given as SOC at cycle 5 or a cumulative dose of 350 mg/m 				
Blood for hscTnI and galectin-3	X	X 				
Blood for BNP 	X	After cumulative dose of 300 mg/m  of doxorubicin, and then every 6 weeks thereafter				
24-hour Holter monitor	X		X			
AE assessment	X	----- X				

1. Women of childbearing potential only
2. Can be drawn with a BMP or CMP if being drawn for routine pre-doxorubicin labs
3. Every 3 months for up to 5 years. Patients who are removed for reasons other than progression will be followed until standard of care imaging shows progression per RECIST 1.1.
4. No more than 30 minutes before SOC doxorubicin
5. With SOC pre-treatment bloodwork and 4 hours post-doxorubicin up until cycle 6
6. Except Cycle 1
7. -3 day window to allow for the echo to be read prior to the start of the next cycle

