## **14.0 STATISTICAL CONSIDERATIONS**

### **14.1 Study Design**

This is a two cohort, open label, nonrandomized study with a noninferiority primary endpoint. The last ten patients enrolled after accrual to the dextrazoxane treatment group has been completed will be considered a control group; the purpose of this group is to obtain control samples for some of the correlative studies. The primary endpoint will be tested only in the active treatment cohort. Toxicity and cardiac function biomarkers will be documented in both cohorts.

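### Secondary objective 3 asks whether 3D echo or strain is an early marker of cardiac dysfunction, but section 14.3 plans only 3D-versus-2D agreement, which leaves timing unanswered and strain without a usable analysis

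*Combined protocol and SAP*

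**What the plan says.** **Question.** Section 2.2, objective 3, is to look at further echo parameters "to determine if either 3D echocardiogram or ventricular strain is able to serve as an early marker of cardiac dysfunction", with 2D modified Simpson's biplane LVEF as the comparator. Section 1.5.1 adds that the newer measures are followed to see whether they predict later deterioration in ejection fraction. Section 9.1 says that 3D ejection fraction and "left ventricular strain, will be used to evaluate for an early or more precise measurement of cardiac dysfunction".

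**Data.** Section 9.1 schedules echocardiograms every six weeks. Sections 10 and 11 place them at baseline and on Day 1 of odd-numbered cycles from Cycle 3. "Left ventricular systolic function will also be evaluated by 3D echocardiogram when technically possible".

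**Analysis.** Section 14.3 has two analyses. One is Kaplan-Meier for cardiac mortality, which serves objective 1. The other is "Agreement between 3D and 2d echocardiogram biomarkers will be described using Bland-Altman plots", with limits at two standard deviations, or bootstrap limits if the values are not Gaussian. Section 14.1 adds only this: "Toxicity and cardiac function biomarkers will be documented in both cohorts". Section 14 does not mention strain.

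**The concern.** An early-marker question is about order in time: did the marker move at a visit before LVEF did? An agreement analysis asks something else, namely whether two methods give the same value at the same visit. The objective names two markers, and the planned analysis covers one of them, on the other question.

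The serial data for a timing analysis will be collected. Without a prespecified analysis, the definition of a change and the way visits are compared would be chosen after the data are seen. With few events, that choice alone could produce or remove an apparent lead. The stake is one of three secondary objectives.

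**Working it through.** The plan gives no figure of its own here, so there is none to reproduce. The core of the point needs no arithmetic; the numbers below only illustrate it.

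**1. Agreement does not use visit order.** With d = 3D minus 2D at one visit, bias = mean(d) and limits = bias ± 2 SD(d). Neither changes if visits are reordered. In a simulated set in which every patient's 3D value fell one visit before 2D, the bias was -1.65 with limits -11.87 to +8.56. Shuffling the visits gave exactly the same three numbers.

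**2. Could bias or width reveal a lead indirectly?** Assumed inputs, none from the documents except the 57 patients (section 14.3.1): baseline plus 4 echoes, full follow-up, reading SD 3.5 points per method, 20% of patients with a 10-point fall, onset equally likely at each of the 4 post-baseline visits, and 3D not falling before the first post-baseline visit.

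- Noise variance of d: 2 × 3.5² = 24.5. No lead: bias 0, half-width 2 × √24.5 = 9.9.
- One-visit lag: each faller has one visit of five with d raised by 10. Bias = 0.20 × 10 / 5 = +0.4. Variance = 24.5 + 0.20 × 100 / 5 - 0.4² = 28.34, half-width 10.6.
- One-visit lead: only 3 in 4 fallers can show it, because an onset at the first post-baseline visit leaves no earlier visit. Bias = -0.20 × 10 × 0.75 / 5 = -0.3. Variance = 24.5 + 0.20 × 100 × 0.75 / 5 - 0.3² = 27.41, half-width 10.5.

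Simulation gives the same values, with a run-to-run SD of the bias of about 0.3. A bias of that size is close to sampling noise, and it could equally be a constant calibration difference between the methods.

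**3. Strain.** Section 1.5.1 describes strain as a measure of myocardial shortening. With assumed values of about 20 for absolute strain and 60 for LVEF, strain minus LVEF gave a bias of about -36 with limits of about -49 to -23. Those figures reflect two different quantities and say nothing about agreement.

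**4. How many falls could a timing table use?** Assume echoes stop at progression (the calendar in section 10 lists none at end of treatment or in follow-up) and PFS is exponential with the 4.6-month median of section 14.3.1. Of 57 patients, 46.3, 37.6, 30.5 and 24.8 are then progression-free at 6, 12, 18 and 24 weeks, a mean of 139.2 / 4 = 34.8. Expected observed falls = rate × 34.8:

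| Assumed fall rate | Observed true falls |
|---|---|
| 3% | 1.0 |
| 7% | 2.4 |
| 20% | 7.0 |
| 27% | 9.4 |

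The span 3% to 27% is the heart-failure range in section 1.3.1. It is borrowed here and is not a rate of LVEF falls. If an event is taken as a 10-point fall from baseline (for illustration, not as a proposed threshold), about 2.4 of 3.1 apparent falls at the 3% rate are reading noise, and about 2 of 6.6 at 20%.

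**5. Would a timing table point the right way?** At a 20% rate with drop-out, the mean number of patients with the marker change earlier versus later than the LVEF event is 0.7 versus 0.7 with no lead, about 1.8 versus 0.6 with a lead, and 0.3 versus 1.5 with a lag. The direction is right, but the counts are very small.

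**The case against.** **The magnitude is assumed throughout.** Fall size, fall rate, reading error and onset pattern are not in the documents, and different assumptions give a different bias (-1.65 in step 1 of the working, -0.3 in step 2). This stands. The figures are illustration only, and the point rests on the mismatch between objective and analysis.

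**The fix may answer little.** With about 1 to 9 true falls, and section 1.4 expecting dexrazoxane to lower cardiomyopathy markedly, the low end is plausible and mostly noise. At a 3% rate, earlier outnumbers later in about 25% of simulated runs with a true lead and 12% with none. This also stands. The result can only be descriptive, which is a reason to fix the definitions in advance and label it so.

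**Strain may be covered by wording.** Section 1.5.1 says strain is obtained from 2D images, so the 2D biomarkers in 14.3 might loosely include it. Even so, an agreement plot against an ejection fraction would be uninformative.

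**Agreement has value.** Section 9.1 speaks of an early or more precise measurement, and agreement partly serves the second aim. A reader might infer that objective 3 has no relevant analysis at all; section 9.1 does not support that.

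**Controls.** A reader might also infer that the controls are a further failure of the echo plan. Sections 1.7 and 9.1 add banking-study controls ("Additional controls for these analyses will be collected from the sarcoma banking study"), and section 10.2 schedules "2D and 3D echocardiogram" for the ten enrolled controls, yet section 14 does not say how either group enters. But 14.1 gives the enrolled group's purpose as control samples for some correlative studies, 9.1 describes a chart review for the banking patients, and nothing shows that the banking patients have 3D or strain readings. This is missing detail and no part of the claim.

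**Conclusion.** The point holds as a mismatch between objective and analysis. Section 2.2 asks about timing for two markers. Section 14 offers a time-blind agreement analysis for one of them, and no other section supplies a method. Followed exactly, the plan leaves the early-marker question unanswered and strain without a usable analysis.

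Two stronger readings should be avoided. A reader might infer that a lead and a lag of the 3D marker give limits of the same width. On the assumed inputs they are close but not equal (half-widths 10.5 and 10.6), and the biases differ in sign. The defect is that neither figure can be read as evidence of order. A reader might also infer that the trial's main result is weakened. It is not: the primary endpoint is PFS in the dexrazoxane cohort and uses no echo data.

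The textual conclusion rests on no assumption. The size figures rest wholly on the inputs listed in the working.

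**What to change.** In section 14.3:

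1. Keep Bland-Altman, stated as the analysis of whether 3D and 2D LVEF are interchangeable, with limits that allow for repeated echoes from the same patient.
2. For 3D LVEF and for strain separately, prespecify a 2D LVEF-decline event and a marker-change event, for analysis only and with no bearing on treatment decisions. Among patients with the LVEF event, tabulate how many had the marker change at an earlier, the same or a later visit, or never. Also count patients with a marker change and no LVEF event.
3. Report how many visits had a readable 3D value and a readable strain value.
4. Label the analysis exploratory and descriptive.

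As a side note, one sentence could say whether and how the controls enter the echo analyses.

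The cost is some wording and a little analyst time, with no added visit or test. The downside is a sparse table: few LVEF events, many entries in the never row, gaps where 3D was not technically possible, and at low fall rates mostly reading noise.
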